7.4. Exploratory endpoints

To demonstrate the efficacy of RT001 on change from baseline at 11 months in clinical symptoms as measured by:

- 1. Modified Friedreich's Ataxia Scale (mFARS)
- 2. Fatigue Symptom Scale (items 2. 4. 7.9 of the total fatigue scale)
- 3. Clinician-rated Clinical Global Impression of Change (CGI-C)
- 4. Activities of daily living (ADL) elements of fatigue scale (items 5,6, 8, 10, and 11)
- 5. Patient Global Impression of Change (PGI-C)
- To evaluate the effects of RT001 on Visual Analogue Scale [VAS]
- To evaluate the effects of RT001 on speech measurements and Speech Assessment questionnaire
- To evaluate the effect of RT001 on T25FW
- To evaluate the effects of RT001 on FARS-Neuro
- To evaluate the effects of RT001 on FARS-ADL.

- To evaluate the effects of RT001 on SF-36
- To evaluate the effects of RT001 on the Neuro-QoL scales (Upper Extremity Function and Lower Extremity Function)
- To evaluate the effects of RT001 on the frequency of falls as reported in a fall diary and subject's fear of falling
- To evaluate the effects of RT001 on the Patient Global Impression of Change (PGI-C) Scale
- To evaluate the effects of RT001 on efficacy assessments after 4 months of treatment
- To evaluate the effects of RT001 on efficacy assessments after 8 months of treatment
- To evaluate the effects of RT001 on ejection fraction as reported in the Echocardiogram
- To evaluate the effects of RT001 on hypertrophy as reported in the Echocardiogram

7.5. Optional Sub-Study Objectives

7.5.1. Optional PK Profile Sub-Study

The objective of the study is to evaluate the pharmacokinetic (PK) profile of RT001 at steady state.

7.5.2. Optional PK Washout Sub-Study

The objective of the study is to evaluate the washout blood levels of RT001 after treatment in RT001-006 is completed.

8. INVESTIGATIONAL PLAN

8.1. Study Design

This is a randomized, double-blind, placebo-controlled study to evaluate the efficacy, safety, and tolerability in subjects with FRDA following the oral administration of study drug (active or placebo capsules).

Subjects will self-administer the study drug orally with meals. While on study drug, subjects are recommended to avoid eating foods high in PUFAs. Subjects will keep food journals from screening through the completion of month 1 on study drug. After month 1, subjects will keep 2-week food journals prior to next scheduled onsite visit. Subjects (or parents/caregivers, as applicable) will have an initial call and as needed with the diet coach to discuss food journal completion requirements.

A total 60 FRDA subjects will be enrolled. Subjects will be randomized to active [9 capsules of RT001 (8.64 g/day) for the first month, followed by 6 capsules of RT001 (5.76 g/day)] or placebo in a 1:1 ratio. Randomization will be stratified by FARS Neurological score: ≤45 and >45. Enrollment of patients with age > 25 will be capped at 25 % of the total enrollment.

Subjects will self-administer orally 9 capsules daily for the first month with a meal: 3 capsules with breakfast, 3 capsules with lunch, and 3 capsules with dinner for the first month. After this initial period the dose will be reduced to 6 capsules daily with a meal: 3 capsules with breakfast, and 3 capsules with dinner for the remainder of the trial, while on study drug. If a subject is unable to tolerate study drug because of adverse events during the initial loading period, the dose may be reduced to six capsules daily (5.76 g total dose) given as 3 capsules with breakfast, and 3 capsules with dinner. If a subject is unable to tolerate study drug because of adverse events after the dose reduction to six capsules daily (5.76 g total dose), the dose may be spread over three meals (2 capsules at breakfast, 2 capsules with lunch, and 2 capsules with dinner). If the subject is still unable to tolerate study drug after spreading it over three meals, the total dose may be reduced by 1-2 capsules/day, preferably by reducing the dose for a meal from 2 to 1 capsule(s) as needed. After 2 weeks of taking a dose of less than 6 caps/day, the subject should try to increase the dose to 6 capsules/day given as 2 capsules TID given with meals. If 6 caps/day is not tolerable, the subject can take the drug at the dose of less than 6 caps/day that was tolerable. The last dose of study drug will be taken at 4 weeks from Day 330 visit.

Participation is anticipated to require 13 months.

- Screening: Up to 30 days from start of treatment
- Treatment Period: treatment for a 12-month period

Safety assessments include physical and neurologic examinations, vital signs, 12-lead electrocardiogram (ECG) tracing, and clinical laboratory tests (hematology, clinical chemistry,

lipid profile, coagulation, and urinalysis) to identify adverse events (AEs). Adverse events will be evaluated for incidence, severity, and relationship to study drug.

The first dose of the study drug will be taken on Day 1. Bioanalytical measurements will be performed to determine the concentration of D2-LA, deuterated arachidonic acid (D2-ARA), nondeuterated linoleic acid (H2-LA) and nondeuterated arachidonic acid (H2-ARA) in plasma and red blood cells. Blood samples will be collected at month 4 (Day 120 ± 30 days), at month 8 (Day 240 ± 30 days), and at month 11 (Day 330 ± 30 days). All samples are to be obtained prior to dosing and prior to breakfast.

Subjects will perform CPET on a stationary recumbent bike at Screening, on Day 1, Day 120 (\pm 30 days), Day 240 (\pm 30 days), and Day 330 (\pm 30 days). Peak work rate and VO₂ MAX will be measured during incremental exercise testing. CPET should occur after fasting (if the subject has had a meal/snack) for a minimum of 2 hours, with neither caffeine nor nicotine for at least 12 hours before testing.

Subjects (with or without assistive device) will perform a T1MW and electronically measured T25FW at Screening, on Day 1, Day 120 (\pm 30 days), Day 240 (\pm 30 days), and Day 330 (\pm 30 days).

CPET and the T1MW/T25FW should be separated in time to allow the subject to recover sufficiently before doing the next test. All tests should be done at approximately the same time and order for each visit.

The FARS-Neuro and clinician-rated CGI scale will be performed at Screening, on Day 1, Day 120 (\pm 30 days), Day 240 (\pm 30 days), and Day 330 (\pm 30 days) by a qualified physician or health professional who is trained on the use of the tool. The CPET examination should always precede the FARS-Neuro evaluation at all visits.

A trained health professional will also work with the subject to perform the speech measurement recording at Screening, on Day 1, Day 240 (\pm 30 days), and Day 330 (\pm 30 days).

The FARS-ADL, SF-36, VAS (for Fatigue), Fatigue scale, Neuro-QoL scales (lower extremity function and upper extremity function) and Fall Questionnaire will be completed by the subjects at screening and at the visits on Day 1, Day 120 (\pm 30 days), Day 240 (\pm 30 days), and Day 330 (\pm 30 days). The PGI-C scale and VAS (for Improvement of FA symptoms) will be completed by all subjects at Day 120 (\pm 30 days), Day 240 (\pm 30 days), and Day 330 (\pm 30 days).

In between the clinic visits, subjects will also be contacted by phone by a study site staff member and asked questions relating to the PGI-C, Fatigue scale, Neuro-QoL Scales (lower extremity function and upper extremity function), and questions 8 and 9 of the fall questionnaire. These phone 'visits' will take place monthly. A Speech Assessment Questionnaire will be completed by the subject and parents/caregiver (as applicable) at Screening, on Day 1, Day 240 (\pm 30 days), and Day 330 (\pm 30 days).

Between clinic visits, subjects will be asked to keep a daily log (diary) documenting falls, nearfalls, stumbles, and fear of falling (Screening through Day 330).

Additional blood samples will be collected and stored for future biomarker analysis on Day 1, on Day 120 (\pm 30 days), Day 240 (\pm 30 days), and Day 330 (\pm 30 days). These samples are to be obtained prior to dosing and prior to breakfast.

A final phone call will occur 4 weeks (+ 7 days) from the Day 330 visit to confirm date of last dose and accountability of final bottles. The site will also collect AE information and confirm any change in concomitant medication since the last visit. Any ongoing AEs at EOT will be followed to conclusion or until stabilized.

Two additional optional sub-studies will be offered. The first is a 24hr PK Profile at steady state that will occur before or after the Day 330 visit. Immediately before or after the Day 330 visit in RT001-006, PK samples will be obtained 30 minutes to 1 hour before the morning dose; and 30 min, 1, 2, 4, 8, 12 and 24 hours after the morning dose.

The second optional sub-study is a 6-month study to evaluate the washout blood levels of RT001 after treatment in RT001-006 is completed. Depending on the timing of entry into the sub-study, washout pharmacokinetic (PK) samples will be obtained at 7 days, 4, 12, and 24 weeks after the last dose to determine the trough concentration of deuterated linoleic acid (D2-LA), deuterated arachidonic acid (D2-ARA), nondeuterated linoleic acid (H2-LA) and nondeuterated arachidonic acid (H2-ARA) in plasma, and D2-LA, D2-ARA H2-LA, and H2-ARA in red blood cells.

8.2. Randomization

The randomized, double-blind design of the study is intended to minimize bias on the part of subjects, investigators, and analysts. Subjects who meet all enrollment criteria and from whom consent has been obtained will be randomly assigned to receive one of two treatments (RT001 or placebo capsules) following a 1:1 ratio. Randomization will be stratified as much as possible according to the FARS Neurological score (baseline FARS score of \leq 45 and >45). Enrollment of patients with age > 25 will be capped at 25 % of the total enrollment.

8.3. Blinding

Subjects and study personnel, including but not limited to investigators, study coordinators, nursing staff, clinical monitors, the Sponsor, and the Sponsor's representatives, will remain blinded to the study treatment assignments (RT001 or placebo).

If there is a need to unblind the study drug assignment for a subject, the Principal Investigator will discuss with the sponsor's Medical Monitor. A separate unblinding plan will document the specific processes related to emergency unblinding. Refer to Section 15.7 for a description of emergency unblinding procedures.

The reason for unblinding must be documented in the source document for the subject. If a subject's study drug assignment is unblinded, the subject should remain in the study and continue the protocol-specified follow-up evaluations.

8.4. Safety Monitoring

8.4.1. Safety Monitoring

The study site investigators assess each subject and record findings obtained during each visit. Subjects will be queried to report any observations, concerns or symptomatology, and a clinical assessment will also be made. This includes any evidence of disease exacerbation and/or progression. Safety reports made during the study (see Section 15) will be promptly reviewed by the Sponsor's Medical Monitor and processed. This includes reporting to the FDA according to 21 CFR 312.32, "IND Safety Reporting," and taking any action necessary to protect subject safety.

8.4.2. Sponsor Safety Monitoring

The blinded safety and efficacy data will be reviewed by the study monitor on an ongoing basis. This data will not be made available to the Principal Investigators unless changes need to be made to the protocol for safety reasons.

8.4.3. Data Safety and Monitoring Board

A Data Safety and Monitoring Board (DSMB) will be established to review this study and provide recommendations per the DSMB Charter.

9. SELECTION AND WITHDRAWAL OF SUBJECTS

9.1. Inclusion Criteria

To be enrolled into the study subjects must meet the following requirements:

- 1. Male or female 12 to 50 years of age
- 2. Medical history consistent with the symptoms of FRDA at \leq 25 years of age
- 3. Detection of biallelic pathogenic variants in frataxin gene (FXN) (i.e. biallelic repeat expansions of GAA in the disease-causing range, or compound heterozygous for a repeat expansion of GAA in the disease-causing range + an intragenic pathogenic variant, etc.)
- 4. Ambulatory (with or without assistive device) and capable of performing other assessments/evaluations
- 5. Must be able to walk 25 feet during the timed 1-minute walk
- 6. Agree to receive calls from a diet coach regarding completion of electronic food journal
- 7. Sign the informed consent form prior to entry into the study
- 8. Agree to stay locally for the required visit days
- 9. Able to provide the necessary repeated blood samples

9.1.1. Inclusion Criteria for Optional PK Profile Sub-Study

- 1. At selected sites, subjects who are enrolled in RT001-006 will be invited to participate in this study.
- 2. All participating subjects will be required to sign an informed consent prior to the collection of the blood draws.
- 3. Subjects must be willing to stay overnight close to the study site and able to provide the necessary repeated blood samples.

9.1.2. Inclusion Criteria for Optional PK Washout Sub-Study

- 1. Subjects who have successfully completed treatment in RT001-006 will be invited to participate in the washout PK sub-study.
- 2. All participating subjects will be required to sign an informed consent prior to any blood draws.
- 3. Subjects must be willing and able to provide the necessary repeated blood samples.

9.2. Exclusion Criteria

Subjects meeting one or more of the following may not enter the study:

- 1. Received treatment with other experimental therapies within the last 30 days prior to the first dose
- 2. Previously participated in the RT001 trial
- 3. Refusal to discontinue fish oils or other oil-based supplements for the duration of the study (Screening till last study procedure completed)
- 4. History of malignancies (other than basal cell carcinomas)
- 5. Inability to complete CPET protocol, as, for example, unable to move the pedals on the exercise bicycle, inability to maintain sufficient RPMs to finish the study, or as judged by the exercise physiologist supervising the testing
- 6. Female who is breastfeeding or has a positive pregnancy test
- 7. Male participant or female participant of childbearing potential, who is sexually active and unwilling/unable to use a medically acceptable and effective double barrier birth control method throughout the study
- 8. Unwilling or unable to comply with the requirements of this protocol, including the presence of any condition (physical, mental, or social) that is likely to affect the subject's ability to return for visits as scheduled
- 9. Clinically significant cardiac abnormalities (e.g., left ventricular ejection fraction [LVEF] <40% on a recent echocardiogram [obtained within 12 months prior to screening] or clinically unstable arrhythmia) at screening that, in the opinion of the Investigator, would make the subject unsuitable for enrollment
- 10. History of or currently uncontrolled diabetes mellitus (Type 1 or 2)
- 11. Suicidal ideation within the last 12 months as determined by the Columbia-Suicide Severity Rating Scale (C-SSRS)
- 12. History, within the last 2 years, of alcohol abuse, significant mental illness, or physical opioid dependence

9.2.1. Exclusion Criteria for Sub-Studies

There are no exclusion criteria for the two additional sub-studies.

9.3. Withdrawal

9.3.1. Withdrawal Criteria

Subjects may choose to withdraw from the study at any time for any reason. In addition, subjects may be withdrawn from the study by the Investigator for any of the following reasons:

• The subject is unwilling or unable to adhere to the protocol.

- During the course of the study, the subject develops symptoms or conditions listed in the exclusion criteria.
- Any SAE, clinically significant AE, severe laboratory abnormality, intercurrent illness, or other medical condition that indicates to the Investigator that continued participation is not in the best interest of the subject.
- Other medical reason, at the discretion of the Investigator and/or the Medical Monitor.

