	12. History, within the last 2 years, of alcohol abuse, significant mental illness, or physical opioid dependence
Food Journal requirement	While on study drug, subjects are recommended to avoid eating foods high in PUFAs. Subjects will keep food journals from screening through the completion of month 1 on study drug. After month 1, subjects will keep 2-week food journals prior to next scheduled onsite visit. Subjects (or parents/caregivers, as applicable) will have an initial call and as needed with the diet coach to discuss food journal completion requirements.
Prohibited Medications	Supplements that contain EPA or DHA are prohibited. Oil-based supplements like Fish oil, Cod Liver oil, Edible algae oil and Flax oil are also prohibited.
Statistical methods	Demographic data will be presented using descriptive statistics (e.g., mean, standard deviation, median, and range). Exposure to study drug and reasons for discontinuation will be tabulated. Safety variables will be tabulated and presented for all subjects who receive study drug or placebo capsules. Adverse events will be coded using the Medical Dictionary for Regulatory Activities (MedDRA). The incidence of treatment-emergent AEs will be presented by system organ class and preferred term. Adverse events will be presented by severity and relationship to

study drug. Changes from Baseline in clinical laboratory parameters and vital signs will be summarized across time. Shift tables will be provided for selected laboratory parameters. Physical examination results will be presented in listings.

Change from baseline (CFB) will be analyzed by comparing the change between treatment groups using a mixed model with repeated measures (MMRM). The MMRM will compare the estimated change from baseline between treatments for the primary endpoint. This analysis will assess whether there is a difference in estimated CFB between active and placebo groups at 11 months.

The primary analysis of percent change from baseline to 11 months in MVO2 as measured by CPET will use the ITT methodology and an MMRM methodology with a random slope and intercept for each individual.

All secondary and exploratory endpoints CFB values will be analyzed using the MMRM Responder analyses will be run on MVO2 (primary), GST, T1MW, Peak Workload, mFARS, and CGI-C (functional assessment). The PK of D2-LA, D2-ARA, H2-LA, and H2-ARA will be characterized in terms of minimum and maximum exposure at steady state.

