7.1. Primary endpoint

1. To demonstrate the efficacy of RT001 compared to placebo on the change of MVO2 in patients with FA through change from baseline to 11 months

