Responder analyses will be run on MVO2 (primary), GST, T1MW, Peak Workload, mFARS, and CGI-C (functional assessment). Responder analyses are performed to illustrate the clinical meaningfulness of the relationship between treatment differences and efficacy outcomes on a per

person basis. Responder analyses will be assessed at change from baseline cutoffs at the overall quartiles for each of the three variables. Patients who die or are unable to perform the test during the study will be counted as non-responders. Patients who do not complete will be carried forward using the last observation carried forward and the imputed value at the study endpoint will be used for the responder analysis.

In addition to summarizing the results for each relationship between individual clinical responses and treatment multiple clinical responses will also be correlated with treatment using the five GST component outcomes individually. Those who experienced the following combined clinical responses will be summarized in terms of counts and percent:

• Improvement or stabilization on at least 1, 2, 3, 4, and all of the 5 responder endpoints.

The PK of D2-LA and H2-LA will be characterized in terms of minimum and maximum exposure at steady state, based on a validated assay. The PK of D2-LA and H2-LA in RBC, D2-ARA, and H2-ARA also will be characterized in terms of minimum and maximum exposure at steady state; the validation of the assays to characterize these concentration values has not yet been validated.

Full details of planned analyses will be provided in a separate statistical analysis plan.

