15. ADVERSE EVENTS

All subjects in the study will have FRDA and the Investigators will take the subjects' Baseline status into account when reporting AEs. Investigators will also consider the underlying disease when designating relationship of AE to study drug, and if AEs are due to the FRDA disease, disease progression or symptomatology exacerbation. Common characteristics of FRDA and RT001 treatment include the following:

- loss of coordination (ataxia) in the arms and legs
- loss of mobility
- fatigue energy deprivation and muscle loss
- vision impairment, hearing loss, and slurred speech
- severe scoliosis
- foot deformities such as clubfoot, flexion of the toes, hammer toes, foot inversion
- diabetes mellitus (insulin-dependent, in most cases)
- hypertrophic cardiomyopathy
- chest pain, shortness of breath, and heart palpitations
- myocardial fibrosis
- heart rhythm abnormalities
- steatorrhea, diarrhea, loose stools

All adverse physical findings/laboratory results identified prior to initiation of study drug will be reported on the medical history and/or physical examination CRFs. After initiation of study drug, any clinically significant changes in physical findings/laboratory results or any new adverse physical findings/laboratory results will be reported as AEs.

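### Section 9.3.1 lets a site end all efficacy follow-up for a subject because that subject can no longer complete CPET, the test behind the primary endpoint

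*Combined protocol and SAP*

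**What the plan says.** Section 9.3.1 is permissive: "subjects may be withdrawn from the study by the Investigator for any of the following reasons". One listed reason is "During the course of the study, the subject develops symptoms or conditions listed in the exclusion criteria". Another is "The subject is unwilling or unable to adhere to the protocol".

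Section 9.2, criterion 5, begins "Inability to complete CPET protocol, as, for example, unable to move the pedals on the exercise bicycle", then adds failure to keep up the pedalling rate and the exercise physiologist's judgement. Unlike criterion 9, which is tied to screening, criterion 5 has no time limit in its wording.

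Section 7.1 defines the primary endpoint as the "change of MVO2 in patients with FA through change from baseline to 11 months". The synopsis confirms the source of the measurement: "The primary analysis of percent change from baseline to 11 months in MVO2 as measured by CPET".

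Once a subject is withdrawn, Section 13.13 lists safety procedures, medication recording and drug accountability. No CPET, walk test, FARS or questionnaire appears. Section 9.3.2 adds telephone follow-up for adverse events. Sections 9.3.4 and 14.2 allow discontinued subjects to be replaced; 9.3.4 limits this to the period before enrolment is complete.

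For the responder analyses, Section 14.1 states: "Patients who die or are unable to perform the test during the study will be counted as non-responders". Its next sentence carries the last observation forward for patients who do not complete. The description of the primary mixed model gives no rule for a CPET that could not be performed, and no sensitivity analysis for values missing for that reason.

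**The concern.** Criterion 5 is a performance criterion. At entry it sensibly screens out people who cannot be measured. Reused during follow-up, it makes failure on the primary test a listed ground for leaving the trial. The failure is foreseeable: under "Common characteristics of FRDA and RT001 treatment include the following", Section 15 names loss of limb coordination, loss of mobility, and fatigue with muscle loss.

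Three things are at stake.

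- **Other endpoints.** A subject who cannot pedal may still be able to walk for a minute, be examined on the FARS and complete questionnaires. T1MW is a named secondary endpoint, and mFARS informs the possible interim re-ordering of endpoints. Withdrawal ends both, along with any later CPET attempt.
- **Missingness that depends on outcome.** Whether later data exist would depend on how badly the subject did, and on whether the site chose to use the rule.
- **Responder scoring.** The same CPET failure could count as a non-response, or could be replaced by an earlier and better value.

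**Working it through.** **1. Reproduce the plan's figure.** Inputs from the synopsis and Section 14.2: mean changes +7.5 and −8.3, SD 11.1, 30 per arm, two-sided alpha 0.05. The difference is 7.5 − (−8.3) = 15.8. The noncentrality is 15.8 / (11.1 × √(2/30)) = 15.8 / 2.866 = 5.51. With 58 degrees of freedom the power is 0.9997, which agrees with the stated figure of over 99%. These inputs are for peak workload. No planning values are given for MVO2.

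**2. Follow one CPET failure through the text.**

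| | Subject kept in study | Subject withdrawn under 9.3.1 |
|---|---|---|
| MVO2 at the failed visit | Missing | Missing |
| Later CPET attempts | Possible | Lost |
| T1MW, FARS, questionnaires | Continue to Day 330 | Lost (9.3.2, 13.13) |
| Responder status (14.1) | Non-responder | Non-responder, or last observation carried forward, depending on which sentence is applied |

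The first row shows that withdrawal does not cause the missing value at the failed visit. The other three rows are what the rule can change.

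**3. Completers only (illustration).** Assume that subjects whose change falls below a common threshold c cannot complete CPET, and that this is a fraction p of placebo. Then c = −8.3 + 11.1·z_p. The mean of those remaining in an arm with mean μ is μ + 11.1·φ(a)/(1 − Φ(a)), where a = (c − μ)/11.1.

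- p = 10%: c = −22.5. Placebo: −8.3 + 11.1 × 0.1755/0.90 = −6.14. Active (0.3% below c): 7.5 + 11.1 × 0.01028/0.9966 = 7.61. Difference 13.8, a loss of 13%.
- p = 20%: c = −17.6. Placebo: −8.3 + 11.1 × 0.2800/0.80 = −4.42. Active (1.2% below c): 7.5 + 11.1 × 0.03068/0.9882 = 7.84. Difference 12.3, a loss of 22%.

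**4. Random-slope model keeping earlier visits (simulation).** This is closer to the planned analysis, though it omits the random intercept, site effect and risk scores. Visits are at Months 4, 8 and 11. Change is a subject slope times month/11 plus visit noise, with total SD 11.1 at Month 11. The share of variance due to slope is assumed to be 50% or 80%. The first visit below the threshold and all later visits are missing. Estimation is by generalised least squares with known variances.

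| Placebo failing | Slope share | Placebo | Active | Difference (true 15.8) | Loss |
|---|---|---|---|---|---|
| 10% | 50% | −6.95 | 7.60 | 14.56 | 8% |
| 10% | 80% | −7.44 | 7.53 | 14.97 | 5% |
| 20% | 50% | −5.87 | 7.69 | 13.56 | 14% |
| 20% | 80% | −6.52 | 7.63 | 14.16 | 10% |

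With an assumed harm of −5.0 in place of a benefit, the same model returns −3.4 to −4.2. In these scenarios the bias is toward no difference in either direction.

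**5. Attribution.** Steps 3 and 4 model the loss of CPET values from subjects who fail CPET. By step 2, the value at the failed visit is missing with or without withdrawal. Retention could recover only later successful attempts, so most of the loss in these tables would remain.

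**The case against.** The strongest reply is that the rule does little to the primary analysis. A subject who cannot pedal has no valid MVO2 at that visit whatever Section 9.3.1 says, and the GST also needs MVO2 and peak workload, so a retained T1MW does not by itself rescue it. This stands, and it limits the claim. A reader might take the 13.8 and 12.3 in the working as the cost of the withdrawal rule. They are not: they are completers-only figures for a different endpoint, and they mostly reflect inability to do the test.

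A reader might also infer that Sections 9.3.1 and 14.1 contradict each other, as if 14.1 assumed such subjects are kept. It does not. Its sentence also covers patients who die, so it is a counting rule that can apply to people who have left. The real gap is that 14.1 does not say which of its two adjacent sentences governs a subject who both failed the test and was withdrawn.

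Other limits also stand. The rule is discretionary, and whether a failed performance test is a developed symptom or condition is open to reading. Subjects must be ambulatory and perform CPET at Screening and Day 1. Criterion 9 is tied to screening, and Section 15 lists diabetes and cardiomyopathy without the qualifiers used in the exclusions, so neither cardiac nor diabetic exclusions add much. Power is not threatened on the planning figures: even 12.3 with 24 against 30 subjects gives noncentrality 12.3 / (11.1 × √(1/24 + 1/30)) = 4.05 and power of about 98%.

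Section 14.1 leaves full details to a separate analysis plan, which could supply the missing rules. The text available does not contain them.

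On frequency, Section 6.4 reports two subjects in RT001-002 who could not start or complete CPET. Against 19 enrolled that is 2/19 = 10.5%, but the section does not say at which visit or in which arm, so it shows only that failure occurs.

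**Conclusion.** The point holds as a gap in data collection and in responder scoring. The protocol allows progression on the primary test to end all later efficacy assessment, leaves the choice to the site, and does not settle how such a subject is scored. The textual link from 9.3.1 to criterion 5 is firm; how often it would be used is unknown.

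The effect on the treatment estimate can only be illustrated. With peak-workload planning values and an assumed 10% to 20% of placebo failing, a true 15.8 becomes about 15.0 to 13.6 in a random-slope model. The failure rate, the common threshold on change and the slope share are all assumptions. Retaining subjects would not remove most of that loss. What retention gains is the T1MW, FARS and questionnaire data, later CPET attempts, and a recorded reason for the missing value. This is a cheap improvement worth making, not a flaw that invalidates the primary comparison.

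**What to change.** 1. **Section 9.3.1.** Add one sentence: inability to complete CPET is not in itself grounds, under any bullet, for ending study visits; the CPET is recorded as unable to perform, and T1MW, FARS and questionnaire assessments, with CPET attempts where feasible, continue to Day 330. It must cover every bullet, because "The subject is unwilling or unable to adhere to the protocol" would otherwise remain a second route to the same withdrawal. The sentence concerns study visits only. Withdrawals for safety and all study-drug decisions are unchanged.
2. **Section 14.1, responder analyses.** State that a recorded inability to perform the test takes precedence over last observation carried forward, whether or not the subject later leaves the study.
3. **Section 14.1, primary analysis.** Add a sensitivity analysis of the primary mixed model that treats MVO2 values missing for this reason as unfavourable, with the handling fixed before unblinding. This step is needed because the first change does not repair the primary analysis.

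The cost is a few lines of text, some visits without a CPET value, and one extra sensitivity analysis.
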